3.8. Instruments used

This study used a form instrument to record the results of observations of research subjects. The form includes informed consent, preoperative assessment results (history taking, physical examination, supporting examination, and tolerance of the study subject's surgery), and postoperative observations (including the amount of bleeding and the blood products transfusion units).

3.9. Research Variables

Table 3.1 Variables in the study.

| Variable Type | Variables |
|--------------------------|---|
| Free | Topical administration of tranexamic acid |
| Bound | 
 ● Number of postoperative hemorrhages 
 ○ Initial bleeding ○ Bleeding 6 hours ○ 24-hour bleeding ○ 48-hour bleeding ● Need for postoperative blood transfusion 
 ○ Packed red cell (PRC) transfusion ○ Platelet transfusion ○ Transfusion of fresh frozen plasma (FFP) ○ Cryoprecipitate transfusion |
| Confounding ⁸ | 
 ● Gender ● Age ● Body mass index ● Concomitant conditions (diabetes mellitus, hypertension) ● Aortic cross-clamp ● Heart-lung bypass machine |

3.10. Operational Definition

Table 3.2 Operational definitions-

| Variables | Definition | Measurement | Variable Scale | Variable Value |
|--|--|---|----------------|--|
| Administration of topical tranexamic acid | Intrapericardial administration of 5 g tranexamic acid in 50 mL 0.9% NaCl after protamine administration and before sternotomy closure in cardiac surgery | - | Nominal | 
 • Treatment (tranexamic acid) • Control (NaCl 0.9%) |
| Amount of bleeding | | | | |
| Initial bleeding | Amount of blood accumulated in the patient's water-sealed drainage (WSD) system shortly after cardiac surgery | Observation of the volume of blood collected in the WSD system | Numerical | mL |
| 6-hour bleeding | Amount of blood accumulated in the water-sealed drainage (WSD) system of a patient 6-hour post cardiac surgery | Observation of the volume of blood collected in the WSD system | Numerical | mL |
| 24-hour bleeding | Amount of blood accumulated in the water-sealed drainage (WSD) system of a patient 24 hour-post cardiac surgery | Observation of the volume of blood collected in the WSD system | Numerical | mL |
| 48-hour bleeding | Amount of blood accumulated in the water-sealed drainage (WSD) system of a patient 48 hours- post cardiac surgery | Observation of the volume of blood collected in the WSD system | Numerical | mL |
| Blood Transfusion Requirements | | | | |
| Packed red cell (PRC) transfusion | Amount of PRC transfusions received in post cardiac surgery patients with Hb levels <10 g/dL to reach Hb levels >10 g/dL before discharge. | Observation of the volume of PRC received by the patient | Numerical | mL |
| Platelet transfusion ⁴⁹ | Amount of blood platelet transfusions received in post cardiac surgery patients with platelets <100,000 U/ μ L to reach levels of 100,000 U/ μ L or in platelet dysfunction. | Observation of the volume of Platelet transfusion received by the patient | Numerical | mL |
| Fresh Frozen plasma (FFP)Transfusion ⁴⁹ | Amount of blood FFP transfusions received by post cardiac surgery patients with international normalized ratio (INR) >1.5 to reach 1.5 | Observation of the volume of FFP received by the patient | Numerical | mL |

| Variables | Definition | Measurement | Variable Scale | Variable Value |
|---|---|--|----------------|---|
| Cryoprecipitate transfusion ⁴⁹ | Amount of cryoprecipitate transfusions received by post cardiac surgery patients with fibrinogen levels <100 mg/dL to reach levels of 100 mg/dL | Observation of the volume of cryoprecipitate received by the patient | Numerical | mL |
| Gender | Patient gender | Data obtained from patient medical records | Nominal | 
 • Male (0) • Female (1) |
| Age | Age of the patient at the time of the procedure | Data obtained from patient medical records | Numerical | year |
| Aortic cross-clamp | Length of use of aortic cross-clamp during surgery | Data obtained from patient medical records | Numerical | minutes |
| Cardiopulmonary Bypass machine (CPB) | Length of time the CPB replaces the patient's circulation during surgery | Data obtained from patient medical records | Numerical | minutes |
| Body Mass Index (BMI) | (Patient's weight in kilograms) squared divided by (Patient's height in meters) at the time of the procedure. | Data obtained from patient medical records | Numerical | kg/m ² |
| Comorbidity | Presence of hypertension and/or diabetes mellitus as comorbidities at the time of the procedure | Data obtained from patient medical records | Nominal | 
 • Hypertension (1) • Diabetes Mellitus (2) |

ription:

WSD: *water-sealed drainage*

PRC: *packed red cell*

FFP: *fresh frozen plasma*

INR: *international normalized ratio*

BMI: Body Mass Index

3.11. Research ethics

The study was approved by the ethics committee at Harapan Kita National Heart Center Hospital, number LB.02.01/VII/040/KEP040/2022, and has received research permit approval with number LB.02.01/XX.2/8186/2022.

3.12. Data processing flow

The data of the research subjects collected using the forms were verified and compiled using SPSS software for Microsoft Windows version 20.0 in the form of descriptive tables. Data normality and statistical analysis for each variable were performed using the same software. The tests used to analyze the two dependent variables (amount of bleeding and blood products transfusion after cardiac surgery) were the independent T-test (for normal data distribution) and the Mann-Whitney test (for abnormal data distribution).

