6.3.2. Effect of tranexamic acid on post-open heart surgery outcomes

Tranexamic acid has been widely used in open-heart surgery to reduce bleeding and the need for post-surgical blood transfusions. Guidelines from the Society of Thoracic Surgeons have recommended using tranexamic acid to reduce bleeding from cardiac surgery (class I recommendation).⁹ The anti-inflammatory profile of tranexamic acid also plays a role in addressing the inflammatory response after cardiac surgery, especially for those using cardiopulmonary bypass. This is because cardiopulmonary bypass carries the risk of coagulopathy, including activation of intrinsic and extrinsic coagulation pathways, platelet dysfunction, and systemic inflammatory response.³⁸ Studies show that low-dose tranexamic acid (10 mg/kg intravenously) is the optimal dose for cardiac surgery.³⁹

Despite its benefits in reducing bleeding and inflammation, several unexpected post-surgical side effects have been reported with tranexamic acid as surgical prophylaxis. The antifibrinolytic profile of tranexamic acid theoretically allows for an increased risk of thromboembolic events such as deep vein thrombosis, early occlusion of vascular implants, cerebral and myocardial infarction, and pulmonary embolism.^{9,10} This is in line with Ross and Salman's meta-analysis, which showed that some patients receiving tranexamic acid prophylaxis and aprotinin (a tranexamic acid analog) experienced thromboembolic events at 1.9% (95% confidence interval 1.1-2.9) and 3.0% (95% confidence interval 1.8-4.6), respectively. However, these events occurred in patients undergoing surgery for subarachnoid

hemorrhage.³⁹

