5.6. Estimated sample size

The number of samples in this study was calculated twice because the dependent variables observed were the amount of bleeding and the need for postoperative blood transfusion, all of which were numerical variables. From the overall calculation results, the largest sample size for this study was taken, then 10% was added to accommodate the possibility of *dropping out*. The formula used in the sample calculation for both variables is the hypothesis test formula for the mean of two independent groups. The literature used as a reference for calculating the sample of this study is a study by Chaudhary et al. (2018).⁴⁴ The following are the sample calculation results for each research variable.

- **A variable amount of bleeding**

$$n_1 = n_2 = 2 \left[\frac{(z_\alpha + z_\beta)s}{(x_1 - x_2)} \right]^2$$
$$n_1 = n_2 = 2 \left[\frac{(1,96 + 0,842)339,021}{300} \right]^2$$
$$n_1 = n_2 = 20,05 \sim 20 \text{ sample}$$

Description:

= normal standard deviation for type I error with α is 0.05 (1.96)

= normal standard deviation for type II error with β is 0.2 (0.842)

= standard deviation between placebo and treatment groups according to the study (placebo = 445.941 mL and treatment = 232.101 mL, so that the mean value taken = 339.021 mL)⁴⁴

= expected clinical difference (taken 300 mL)

- **Variable blood transfusion needs**

$$n_1 = n_2 = 2 \left[\frac{(z_\alpha + z_\beta)s}{(x_1 - x_2)} \right]^2$$

$$n_1 = n_2 = 2 \left[\frac{(1,96 + 0,842)1,072}{1} \right]^2$$

$$n_1 = n_2 = 18,04 \sim 18 \text{ sample}$$

Description:

= average standard deviation for type I error with α is 0.05 (1.96)

= average standard deviation for type II error with β is 0.2 (0.842)

= standard deviation between placebo and treatment groups according to the study (placebo = 1.225 units and treatment = 0.918 units so that the mean value taken = 1.072 units)⁴⁴

= expected clinical difference (taken as 1 unit)

Based on the above calculation results, 20 patients were taken as the minimum sample size for each placebo and treatment group. With the addition of 10% to anticipate dropouts (2 patients per group), the total sample for each group was 22 samples. The total sample for both groups was 44 patients. In this study, there are three arms group (CABG group, OPCAB group, and Valve Surgery group). The total sample for both arms group was 132 patients.

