1.4 Detailed cost plan

| | |
|--|------------------------|
| Proposal drafting (printing and photocopying costs) | Rp600.000,00 |
| Submission of ethics and research permits | Rp900.000,00 |
| Data collection (observation, consumables) | Rp15.000.000,00 |
| Preparation of research report (printing and photocopying costs) | Rp1.500.000,00 |
| Journal publication | Rp5.000.000,00 |
| Total | Rp23.000.000,00 |

1.5 *Dummy table*

Tabel Error! No text of specified style in document..1 Sample table of experimental and control group characteristics

| Variables | Experimental Group | Control Group (Placebo) | P-value |
|---------------------------------------|--------------------|-------------------------|---------|
| Age (years) | Rerata ± SD | Rerata ± SD | |
| Gender | | | |
| Male | n (%) | n (%) | |
| Women | n (%) | n (%) | |
| Body surface area (m ²) | Mean ± SD | Mean ± SD | |
| Comorbidities | | | |
| Hypertension | n (%) | n (%) | |
| Diabetes mellitus | n (%) | n (%) | |
| Preoperative hemoglobin | Mean ± SD | Mean ± SD | |
| Preoperative hematocrit | Mean ± SD | Mean ± SD | |
| Preoperative APTT | Mean ± SD | Mean ± SD | |
| Preoperative INR | Mean ± SD | Mean ± SD | |
| Preoperative creatinine | Mean ± SD | Mean ± SD | |
| Postoperative hemoglobin | Mean ± SD | Mean ± SD | |
| Duration of aortic cross clamp | Mean ± SD | Mean ± SD | |
| Duration of use of heart-lung machine | Mean ± SD | Mean ± SD | |

Tabel Error! No text of specified style in document..2 Sample output table of CABG results in experimental and control groups

| Primary outcome output | Control group (n=22) | Experimental group with TXA (n = 22) | P-value |
|----------------------------------|----------------------|--------------------------------------|---------|
| Volume of chest drain bleeding | | | |
| Initial bleeding (mL) | Mean ± SD | Mean ± SD | |
| 6-hour bleeding (mL) | Mean ± SD | Mean ± SD | |
| 24-hour bleeding (mL) | Mean ± SD | Mean ± SD | |
| 48-hour bleeding (mL) | Mean ± SD | Mean ± SD | |
| Blood Transfusion | | | |
| PRC transfusion (mL) | Mean ± SD | Mean ± SD | |
| FFP transfusion (mL) | Mean ± SD | Mean ± SD | |
| TC transfusion (mL) | Mean ± SD | Mean ± SD | |
| Cryoprecipitate transfusion (mL) | Mean ± SD | Mean ± SD | |

Table Error! No text of specified style in document..3 Sample output table of OPCAB results in experimental and control groups

| Primary outcome output | Control group (n=22) | Experimental group with TXA (n = 22) | P-value |

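### The plan names and records six confounders, but its bleeding tests cannot use them; this costs precision and protection against chance imbalance, not validity

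*Combined protocol and SAP*

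**What the plan says.** Table 3.1 (section 3.9) has a row for confounding variables: gender, age, body mass index, "Concomitant conditions (diabetes mellitus, hypertension"), aortic cross-clamp and heart-lung bypass machine. Table 3.2 (section 3.10) defines each one, taken from the medical record; cross-clamp and bypass are durations in minutes.

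The only inferential text is in section 3.12. The tests for the amount of bleeding and for transfusion "were the independent T-test (for normal data distribution) and the Mann-Whitney test (for abnormal data distribution". No regression, ANCOVA, stratified test or sensitivity analysis appears anywhere. Section 3.7.1 (Before surgery) describes randomisation by a web site, with no stratification or blocking on these factors.

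In the dummy tables (section 1.5) most of these variables appear once, in a characteristics table with a P-value column, for example "Duration of use of heart-lung machine". BMI is not there; body surface area stands in its place. The outcome tables give mean ± SD and a P-value for 22 against 22 in each surgery group, with no adjusted estimate.

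The literature review (section 6.3.2) says that "cardiopulmonary bypass carries the risk of coagulopathy".

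**The concern.** The plan identifies variables that it expects to influence bleeding, collects them, and then uses an analysis that leaves them all in the error term. The hypotheses in section 1.4 are separate for CABG, OPCAB and valve surgery, so each bleeding question rests on 44 patients. At that size chance differences between arms in age, body size or bypass time are common, and the plan offers no adjusted estimate to show whether such a difference matters. If no covariates are named in advance, any adjustment added later would be open to choice after the results are seen. This point concerns the bleeding hypotheses only.

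**Working it through.** **Inputs (section 5.6).** Two-sided alpha: "normal standard deviation for type I error with α is 0.05 (1.96"). Power: "normal standard deviation for type II error with β is 0.2 (0.842"). Target difference 300 mL. Arm SDs 445.941 and 232.101 mL, "so that the mean value taken = 339.021 mL". Group size 22 per arm per surgery type. The documents tie neither the SDs nor the 300 mL to one of the four bleeding time points; I assume that they apply to the one chosen for analysis.

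**The plan's own figure.** n = 2 × [(1.96 + 0.842) × 339.021 / 300]² = 20.05. The plan takes 20, adds 10% to reach 22 per arm, and 22 × 2 × 3 = 132. This reproduces.

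**Chance imbalance.** The arm difference in a continuous covariate, in units of its own SD, has standard deviation √(2/22) = 0.302. So P(|difference| > 0.3 SD) = 32% and P(|difference| > 0.5 SD) = 9.7%, for any one covariate.

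**Power at 22 per arm, difference 300 mL.** Two SDs are shown: the plan's 339 mL (simple mean of the arm SDs) and √((445.941² + 232.101²)/2) = 355.5 mL (root mean square).

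- Unadjusted SE = SD × √(2/22): 102.2 mL and 107.2 mL.
- Adjusted SE with k = 2 covariates = SD × √(2/22) × √(1 − R2) × √(41/39), where 41/39 = (2n − 3)/(2n − 3 − k) is the price of estimating two slopes. Degrees of freedom: 44 − 2 − 2 = 40.
- Power is from the noncentral t distribution. R2 is an assumption.

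| Analysis | SE, SD 339 | Power, SD 339 | SE, SD 355.5 | Power, SD 355.5 |
|---|---|---|---|---|
| Unadjusted t-test | 102.2 | 81.8% | 107.2 | 78.1% |
| Two covariates, R2 = 0 | 104.8 | 79.8% | 109.9 | 75.9% |
| R2 = 0.10 | 99.4 | 83.7% | 104.3 | 80.2% |
| R2 = 0.20 | 93.7 | 87.8% | 98.3 | 84.6% |
| R2 = 0.30 | 87.7 | 91.6% | 91.9 | 88.9% |

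**Break-even.** Precision is unchanged when (1 − R2) × 41/39 = 1, so R2 = 2/41 = 4.9%. With seven terms (all listed variables, hypertension and diabetes separate) it is 7/41 = 17%, which is why the model should be short.

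**Validity.** In simulation with R2 = 0.3, type I error was 5.0% for the unadjusted test and 5.2% for the adjusted one.

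**Choice of standard error.** The assumed arm SDs differ almost twofold, so robust standard errors are sensible, but the type matters. In simulations with SDs 446 and 232 mL, 22 per arm and two covariates, HC1 and HC2 with a t reference match the SD 355.5 column and keep type I error near 5%. HC3 gives about 73% power at R2 = 0 and 77% at R2 = 0.10, below the unadjusted 78%. HC0 raises type I error to about 6.5%.

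**The case against.** The strongest reply is that a randomised comparison needs no adjustment. Chance imbalance is already part of the t-test's standard error, and its type I error is correct. That stands. Because Table 3.1 uses the word confounding, a reader might infer that the unadjusted result is biased. The documents do not support that: allocation is random, so these are prognostic factors whose imbalance is a matter of chance. Even a 0.5 SD imbalance in a covariate correlated 0.3 to 0.5 with bleeding (assumption) shifts the difference by 0.5 × r × 355.5 = 53 to 89 mL, which is within one standard error (107 mL).

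A reader might also multiply the 10% chance across all six variables and expect a marked imbalance in nearly half of the surgery groups. That does not hold. By the protocol's definition OPCAB uses no bypass, so it has four usable variables (1 − 0.903⁴ = 34%, if independent). Clamp and bypass times are unlikely to be independent of each other. A two-covariate model addresses only two of them (1 − 0.903² = 18.5%). Nor is it useful to quote the power of the P-values in the characteristics table: randomisation rules out a true difference between arms, and what matters is the imbalance observed.

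R2 is unknown, and at R2 = 0.10 the gain is only about 2 points; this too stands. Support for bypass duration is indirect, since section 6.3.2 speaks of being on bypass, not of minutes. Bypass time is also recorded after randomisation. But in the CABG and valve groups section 3.7.2 places the study solution after the machine has stopped, so under blinding the solution cannot affect it.

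The row for "Postoperative hemoglobin" in the characteristics table, and the P-value column there, are minor matters of presentation.

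**Conclusion.** The point holds as one of efficiency and protection against chance imbalance, not of validity. The plan lists and records prognostic variables and specifies no analysis that can use them. If two well-chosen covariates explain 20 to 30% of the variance in bleeding (assumption), adjustment cuts the standard error by about 8 to 14% and raises power from 82% to 88–92% at the plan's SD, or from 78% to 85–89% at SD 355.5 mL. If they explain nothing, about 2 points are lost. The figures assume 22 evaluable patients per arm, roughly normal volumes, and SDs that apply to the chosen time point. With 20 evaluable per arm and SD 355.5 mL the pattern is the same at a lower level: 74% unadjusted, and 71%, 76%, 81% and 86% at R2 = 0, 0.10, 0.20 and 0.30.

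**What to change.** In section 3.12, for each surgery group:

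1. Name one bleeding time point for this analysis, for example 24-hour drain volume.
2. Pre-specify a linear model of that volume on arm plus two covariates from Table 3.1, for example BMI and bypass time in CABG and valve, and BMI and age in OPCAB.
3. Before BMI is used, correct its definition in Table 3.2, which squares weight, to weight divided by height squared. Show BMI in the characteristics table, which now has body surface area.
4. Report the adjusted mean difference with 95% CI, using HC1 or HC2 standard errors (named in the text) and a t reference.
5. State in advance that volume is log-transformed if strongly skewed, and how that is judged; the result is then a ratio of geometric means.
6. Keep the planned unadjusted test as a sensitivity analysis.
7. State that covariates are not chosen by the P-values in the characteristics table.

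The cost is a few lines of text and a row for the adjusted estimate in the outcome tables, with no new data. The risk is about 2 points of power if the covariates are unrelated to bleeding.

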3.13. Research flow

[figure not shown]

Table 3.3 Research protocol

| TIME | LOCATION | ACTION |
|-------------|-----------------|---|
| D-1 | Preoperative | 
1. Patient's informed consent, signature on a consent form2. Put a green research sticker on the patient's status3. Ensure STOP ACE inhibitors (Captopril, Ramipril, Lisinopril) and ARBs (Candesartan, Valsartan) 24 hours preoperatively.4. Make sure to STOP antiplatelet drugs 3-7 days preoperatively5. Make sure to STOP Warfarin 4-5 days preoperatively6. Ensure Heparin STOP 4-6 hours preoperatively7. Ensure STOP LMWH 12-48 hours preoperatively8. Record all required patient data on the questionnaire |
| D+0 | Operating Room | 
1. Induction, intubation2. Standard operating procedures3. The surgeon administers topical tranexamic acid (5 g in 50 mL NS) or placebo in 100 mL, 50 mL after protamine administration, and 50 mL before closing the sternum.4. Chest tube clamps should not be opened until the skin closure process is complete. |
| D+0 | ICU | 
1. Calculate the initial bleeding when the patient arrives at the intensive care unit2. Collect blood coagulation examination data (blood, hematocrit, PT/APTT, INR)3. Count the amount of bleeding from the chest tube in the first 6 hours and 24 hours4. Disconnect the chest tube if the amount of bleeding is <200 mL in 24 hours |
| D+1 | ICU | 
1. Count the amount of bleeding from the chest tube in the second 24 hours (if the chest tube is still in place)2. Chest tube removal when the amount of bleeding is <200 mL in the second 24 hours |

| TIME | LOCATION | ACTION |
|--------------------------|----------------|---|
| | | 3. Calculate the use of blood component transfusion (PRC, FFP, TC, Cryoprecipitate) |
| D+2 – hospital discharge | ICU - Wardroom | 1. Record clinical output results according to the questionnaire (total amount of drain production and transfusion use of blood components) |

1.3 Research schedule

| Activities | 2022 | | |
|--|---------|----------|----------|
| | October | November | Desember |
| Submission of research ethics approval | X | | |
| Data collection and retrieval | | X | |
| Data processing and hypothesis testing | | | X |
| Preparation of research report | | | X |

1.4 Detailed cost plan

| | |
|--|------------------------|
| Proposal drafting (printing and photocopying costs) | Rp600.000,00 |
| Submission of ethics and research permits | Rp900.000,00 |
| Data collection (observation, consumables) | Rp15.000.000,00 |
| Preparation of research report (printing and photocopying costs) | Rp1.500.000,00 |
| Journal publication | Rp5.000.000,00 |
| Total | Rp23.000.000,00 |

1.5 *Dummy table*

Tabel Error! No text of specified style in document..1 Sample table of experimental and control group characteristics

| Variables | Experimental Group | Control Group (Placebo) | P-value |
|---------------------------------------|--------------------|-------------------------|---------|
| Age (years) | Rerata ± SD | Rerata ± SD | |
| Gender | | | |
| Male | n (%) | n (%) | |
| Women | n (%) | n (%) | |
| Body surface area (m ²) | Mean ± SD | Mean ± SD | |
| Comorbidities | | | |
| Hypertension | n (%) | n (%) | |
| Diabetes mellitus | n (%) | n (%) | |
| Preoperative hemoglobin | Mean ± SD | Mean ± SD | |
| Preoperative hematocrit | Mean ± SD | Mean ± SD | |
| Preoperative APTT | Mean ± SD | Mean ± SD | |
| Preoperative INR | Mean ± SD | Mean ± SD | |
| Preoperative creatinine | Mean ± SD | Mean ± SD | |
| Postoperative hemoglobin | Mean ± SD | Mean ± SD | |
| Duration of aortic cross clamp | Mean ± SD | Mean ± SD | |
| Duration of use of heart-lung machine | Mean ± SD | Mean ± SD | |

Tabel Error! No text of specified style in document..2 Sample output table of CABG results in experimental and control groups

| Primary outcome output | Control group (n=22) | Experimental group with TXA (n = 22) | P-value |
|----------------------------------|----------------------|--------------------------------------|---------|
| Volume of chest drain bleeding | | | |
| Initial bleeding (mL) | Mean ± SD | Mean ± SD | |
| 6-hour bleeding (mL) | Mean ± SD | Mean ± SD | |
| 24-hour bleeding (mL) | Mean ± SD | Mean ± SD | |
| 48-hour bleeding (mL) | Mean ± SD | Mean ± SD | |
| Blood Transfusion | | | |
| PRC transfusion (mL) | Mean ± SD | Mean ± SD | |
| FFP transfusion (mL) | Mean ± SD | Mean ± SD | |
| TC transfusion (mL) | Mean ± SD | Mean ± SD | |
| Cryoprecipitate transfusion (mL) | Mean ± SD | Mean ± SD | |

Table Error! No text of specified style in document..3 Sample output table of OPCAB results in experimental and control groups

| Primary outcome output | Control group (n=22) | Experimental group with TXA (n = 22) | P-value |
|--|-------------------------|---|---------|
| Volume of chest drain bleeding | | | |
| Initial bleeding (mL) | Mean ± SD | Mean ± SD | |
| 6-hour bleeding (mL) | Mean ± SD | Mean ± SD | |
| 24-hour bleeding (mL) | Mean ± SD | Mean ± SD | |
| 48-hour bleeding (mL) | Mean ± SD | Mean ± SD | |
| Blood Transfusion | | | |
| PRC transfusion (mL) | Mean ± SD | Mean ± SD | |
| FFP transfusion (mL) | Mean ± SD | Mean ± SD | |
| TC transfusion (mL) | Mean ± SD | Mean ± SD | |
| Cryoprecipitate transfusion (mL) | Mean ± SD | Mean ± SD | |

Table Error! No text of specified style in document..4 Sample output table of valve surgery results in experimental and control groups

| Primary outcome output | Control group (n=22) | Experimental group with TXA (n = 22) | P-value |
|--|-------------------------|---|---------|
| Volume of chest drain bleeding | | | |
| Initial bleeding (mL) | Mean ± SD | Mean ± SD | |
| 6-hour bleeding (mL) | Mean ± SD | Mean ± SD | |
| 24-hour bleeding (mL) | Mean ± SD | Mean ± SD | |
| 48-hour bleeding (mL) | Mean ± SD | Mean ± SD | |
| Blood Transfusion | | | |
| PRC transfusion (mL) | Mean ± SD | Mean ± SD | |
| FFP transfusion (mL) | Mean ± SD | Mean ± SD | |
| TC transfusion (mL) | Mean ± SD | Mean ± SD | |
| Cryoprecipitate transfusion (mL) | Mean ± SD | Mean ± SD | |

REFERENCE

1. World Health Organization (WHO). Global health estimates 2016: deaths by cause, age, sex, by country and by region, 2000-2016 [Internet]. Geneva: World Health Organization; 2018. Diunduh dari: www.who.int/healthinfo/global_burden_disease/estimates/en/
2. World Health Organization (WHO). Noncommunicable diseases (NCD) country profiles – Indonesia. Geneva: World Health Organization; 2018.

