1.4. Hypothesis

1. There was a difference in mean bleeding volume between patients given topical tranexamic acid versus placebo in patients after coronary artery bypass surgery (CABG).
2. There was a difference in mean bleeding volume between patients given topical tranexamic acid versus placebo in patients after off-pump coronary artery bypass (OPCAB).
3. There was a difference in mean bleeding volume between patients given topical tranexamic acid versus placebo in patients after heart valve surgery.
4. There was a difference in mean blood product transfusion requirements between patients given topical tranexamic acid versus placebo in patients after coronary artery bypass surgery (CABG).
5. There was a difference in mean blood product transfusion requirements between patients given topical tranexamic acid versus placebo in patients after off-pump coronary artery bypass (OPCAB).
6. There was a difference in mean blood product transfusion requirements between patients given topical tranexamic acid versus placebo in patients after heart valve surgery.

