3.7.3. Post-surgery

Patients were intensively treated in the intensive care unit (ICU), intermediate room, and standard room according to clinical conditions. The researcher observed and recorded the amount of bleeding accumulated until chest tube removal and blood products transfusion units of blood components during treatment. Transfusion will be given when there is an indication for transfusion. The indication for *packed red cell* (PRC) transfusion was Hb <10 g/dL, with a target of Hb >10 g/dL. The indication for platelet transfusion was platelets <100,000 U/ μ L, with a target of platelets >100. The indication for fresh frozen plasma (FFP) transfusion is if APTT > 1.5 times the control, the transfusion target is activated partial thromboplastin clotting time (APTT) < 1.5 times the control. Cryoprecipitate was given if fibrinogen < 100 mg/dL, and the transfusion target was fibrinogen > 100 mg. Observation of bleeding was recorded from initial

bleeding, 6 hours, 24 hours, and 48 hours, or until chest tube removal if the bleeding was <200 mL/24 hours.

Bleeding management protocols were performed if there was excessive or massive bleeding post-surgery. A single researcher conducted all observations to maintain data reliability which was then recorded for further processing.

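### Eight rows per surgery group are labelled primary, no visible text says which decides the bleeding or the transfusion hypothesis, and no row matches the transfusion endpoint that was sized

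*Combined protocol and SAP*

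**What the plan says.** Section 1.4 gives two hypotheses per surgery group. The first for CABG reads "There was a difference in mean bleeding volume between patients given topical tranexamic acid versus placebo in patients after coronary artery bypass surgery (CABG"; its transfusion counterpart concerns mean blood product requirement. Neither names a time point or a product.

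Section 5.6 takes the same two-variable view: "the dependent variables observed were the amount of bleeding and the need for postoperative blood transfusion". Bleeding is sized on 300 mL with no time point. Transfusion is sized on an "expected clinical difference (taken as 1 unit", with no product named.

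Table 3.1 (section 3.9) divides the bleeding variable, there called "Number of postoperative hemorrhages", into initial, 6-hour, 24-hour and 48-hour values, and transfusion into four products. Table 3.2 (section 3.10) defines every product as a volume in mL. Section 3.7.3 also records the "amount of bleeding accumulated until chest tube removal", a fifth candidate for the bleeding outcome.

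The three outcome tables in section 1.5 list all eight measures under "Primary outcome output | Control group (n=22) | Experimental group with TXA (n = 22) | P-value". There is no row for total transfusion and none in units.

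The analysis text is section 3.12: "The tests used to analyze the two dependent variables (amount of bleeding and blood products transfusion after cardiac surgery) were the independent T-test", with the Mann-Whitney test for non-normal data. It gives no significance level, deciding row, order or correction.

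**The concern.** With two hypotheses and eight rows called primary, the row that settles each hypothesis can be picked after the results are known. One favourable time point or one product could then be reported as confirming the group's hypothesis at 5%, when the chance of at least one such result with no drug effect is higher.

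The transfusion hypothesis has a further problem: the quantity that was sized appears in no table, so even a reader who wants to hold the trial to its own sizing cannot tell which result to look at.

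The P-value column alone is weak evidence, because the baseline table has one too. The fault lies in the primary label over eight rows with nothing elsewhere to choose among them.

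**Working it through.** **1. The plan's sizing (section 5.6).** Formula: n per arm = 2[(z_α + z_β)s/Δ]², with z_α = 1.96 and z_β = 0.842.

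- Bleeding, s = 339.021 mL, Δ = 300 mL: 2 × (2.802 × 339.021/300)² = 20.05; the plan says 20.
- Transfusion, s = 1.072 units, Δ = 1 unit: 2 × (2.802 × 1.072)² = 18.04; the plan says 18.
- 20 + 2 for dropout = 22 per arm; 22 × 2 × 3 = 132.

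The figures reproduce. Each calculation spends 0.05 on a single outcome.

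**2. Matching hypothesis, sizing and table.**

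| | Hypothesis (1.4) | Sized as (5.6) | Rows labelled primary (1.5) |
|---|---|---|---|
| Bleeding | mean volume, no time | mL, no time | 4 times, mL |
| Transfusion | mean requirement, no product | units, no product | 4 products, mL, no total |

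For bleeding, four rows could be the sized endpoint. For transfusion, none is. Section 3.8 says the form holds "postoperative observations (including the amount of bleeding and the blood products transfusion units", so units may be collected, but Table 3.2 defines mL.

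**3. Chance of at least one false positive in one surgery group, no drug effect.** Assumptions: each row is tested two-sided at 0.05 (a level stated only in the sizing), and any one significant row counts. For k independent tests the rate is 1 − 0.95^k. For correlated tests it was simulated with equal correlation r (1,000,000 draws). The documents give no correlations, so a range is shown.

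| r | 8 rows | 4 bleeding times | 2 outcomes |
|---|---|---|---|
| 0 | 33.7% | 18.5% | 9.75% |
| 0.5 | 24.9% | 15.5% | 9.1% |
| 0.7 | 19.1% | 13.1% | 8.3% |
| 0.9 | 11.9% | 9.4% | 7.1% |
| 0.95 | 9.6% | 8.0% | 6.4% |

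Simulated t-tests at 22 per arm agree to within about 0.4 percentage points (for example 25.3% and 12.1% for eight rows at 0.5 and 0.9). A mixed pattern, 0.8 among bleeding times and 0.3 elsewhere, gives about 26%.

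**4. Error rules once one row per hypothesis is named.** Simulated t-tests, 20 per arm, both sized effects present, correlations 0 to 0.9:

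| Rule | Joint error | Bleeding power | Transfusion power |
|---|---|---|---|
| Separate claims, each 0.05 | about 7–10% | 78% | 82% |
| Holm | at most 5% | about 74–75% | 76–79% |
| Fixed order, bleeding first | 5% | 78% | 64–75% |

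If the drug changed transfusion but not bleeding, Holm would confirm transfusion in about 73% of trials; the fixed order would do so in at most 5%.

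**The case against.** - **The excess is conditional.** It arises only if one significant row may be read as success. The plan does not say so, and 0.05 appears only in the sizing. This stands, and the claim is worded accordingly. But the plan states no opposite rule either, such as requiring all rows to be significant.
- **A reader might infer a false-positive rate of 34%.** The documents do not support that. It needs eight independent tests, whereas Table 3.2 defines the bleeding rows as accumulated volumes from the same drain. It is an upper bound. Strong correlation shrinks the excess but does not remove it: eight rows still give 9.6% at 0.95.
- **A reader might infer that bleeding and transfusion must share one 5%.** Section 1.4 numbers them as separate hypotheses. If each is reported as its own claim, each keeps its own 5%, and the 7–10% joint rate is something to disclose, not an error in itself. For the same reason, testing transfusion only after a significant bleeding result is a choice with a real cost, not a requirement.
- **The mL/units mismatch is a separate fault.** It adds nothing to the error rate and would need repair even with one primary row. It belongs here because a deciding transfusion row cannot be named without resolving it.
- **Some figures, including the research flow, are not shown.** Hence the claim is that no visible text names a deciding row.

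**Conclusion.** The point holds in conditional form. Each surgery group has one bleeding and one transfusion hypothesis but eight rows labelled primary, with no visible rule for choosing among them. If any single row at 0.05 may confirm, the per-group false-positive rate is about 8–16% across the four bleeding times and about 10–25% across all eight rows. Those ranges rest on assumed equal correlations of 0.95 down to 0.5. The transfusion endpoint that was sized has no row in any table; that finding depends on no assumption about correlation.

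The documents do not support calling the sample size miscalculated, since it reproduces from its own inputs. Nor do they show that error is inflated whatever the reporting rule. The point is still worth fixing before analysis, because it settles what each surgery group's result can be said to show.

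**What to change.** Before any unblinded data are seen, for each surgery group:

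1. Name one deciding bleeding row. Cumulative drain volume at 24 hours is a reasonable choice, because Table 3.3 counts second-day drainage only while the tube is still in place. Another time could be justified.
2. Name one deciding transfusion total, stating the products counted, the time window and the unit. Add that row to the tables and align the sizing with it. Check first that the form captures units; if it captures only mL, restate the sizing in mL.
3. Relabel the remaining times and products as secondary, with confidence intervals and no superiority claim.
4. State the error rule for the two deciding outcomes: separate claims at 0.05 with the joint rate of about 7–10% disclosed, or joint 5% control by Holm or by fixed order.
5. State that error is controlled within each surgery group only.

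The cost is analysis wording, table headings and one added row; no extra patients. The other rows lose primary status. Under joint control power falls as tabulated: a few points for each outcome with Holm, or from 82% to 64–75% for transfusion alone with the fixed order. The bleeding power figures assume that 300 mL and SD 339 mL apply at the named time, which section 5.6 does not say.

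Section 1.3 (research schedule) places hypothesis testing in December 2022. If results have already been seen, a row named now is not pre-specified and must be reported as such.
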